6.1.12 Criteria for Participant Termination

Participants MUST discontinue the IP (and non-investigational product at the discretion of the SI) for any of the following reasons:

- Withdrawal of informed consent (participant's decision to withdraw for any reason)
- Any clinical adverse event (AE), laboratory abnormality or intercurrent illness which, in the opinion of the SI or sponsor, indicates that continued participation in the study is not in the best interest of the participant

- Disease progression, which, in the opinion of the SI or sponsor, indicates that continued participation in the study is not in the best interest of the participant
- Pregnancy
- Termination of the study by the Sponsor
- Loss of ability to freely provide consent through imprisonment or involuntary incarceration for treatment of either a psychiatric or physical (e.g., infectious disease) illness

All participants who discontinue study treatment earlier than Week 24 should comply with protocol specified Early Termination procedures as appropriate, outlined in the Schedule of Activities.

An exception to the requirement for End of Treatment procedures is when a participant withdraws consent for all study procedures or loses the ability to consent freely (i.e., is imprisoned or involuntarily incarcerated for the treatment of either a psychiatric or physical illness).

6.2 Open Label Extension (OLE)

Participants who have completed the placebo-controlled portion of the trial on drug, will be eligible to continue in the Open Label Extension. The OLE of the study will continue until verdiperstat is approved and available in the United States, or Biohaven Pharmaceuticals terminates development of verdiperstat for ALS.

Modifications to OLE Schedule

Designated visits in the Schedule of Activities for the OLE (i.e. Week 4, Week 8, Week 16, Week 28, and Week 40) may be conducted via telemedicine (or phone if telemedicine is not available) with remote services instead of in-person if needed to protect the safety of the participant due to a pandemic or other reason. If a planned in-clinic visit is conducted via telemedicine (or phone if telemedicine is not available) with remote services, only selected procedures will be performed. Instructions on how to document missed procedures are included in the Manual of Procedures.

In addition to the procedures in the Master Protocol that should be conducted during the phone or telemedicine and remote visits, the following regimen-specific procedures should be completed:

- Home Spirometry
- CNS Bulbar Function Scale (Week 8 and 16 only).

Blood samples for Week 16 PK and PD analysis and the Week 4 and 28 ECGs are **not** collected during the remote visits by the home health agency and this should be recorded as such in the applicable source documentation and EDC.

6.2.1 Week 2 Telephone Visit - OLE

This visit (via telephone) will take place 14 ± 3 days after the Week 24 visit. The procedures listed in the SoA should be performed including:

- Assess and document AEs and concomitant medications, including Key Study Events (see section 10.3 of Master Protocol)
- Assess compliance and tolerance to this dose titration schedule
 - If tolerability issues are experienced with 300 mg QD or 300 mg BID dosing, the titration schedule may be modified (see Section 5.3.2).
- Instruct participants on appropriate dosing
 - Starting at the beginning of Week 3, to ingest 600 mg BID of verdiperstat and continue taking this dose through the remainder of the 52-week OLE
- Remind participant to bring in IP to the next visit

6.2.2 Week 4 Visit – OLE

This visit will take place in-person 28 ± 10 days after the Week 24 Visit of the placebo-controlled portion of the trial. The procedures listed in the SoA should be performed and participants should be provided with 4 weeks of drug and instructions for dosing.

6.2.3 Week 8 Visit - OLE

This visit will take place in-person 56 ± 7 days after the Week 24 Visit of the placebo-controlled portion of the trial. The procedures listed in the SoA should be performed and participants should be provided with 8 weeks of drug and instructions for dosing.

6.2.4 Week 12 Telephone Visit – OLE

This visit will take place 84 ± 3 days after the Week 24 Visit of the placebo-controlled portion of the trial via telephone. The procedures listed in the SoA should be performed.

6.2.5 Week 16 Visit – OLE

Participants should be instructed to skip the morning dose of study drug on the day of the study visit. Study drug should not be taken until after study visit procedures are complete.

This visit will take place in-person 112 ± 7 days after the Week 24 Visit of the placebo-controlled portion of the trial. The procedures listed in the SoA should be performed and participants should be provided with 12 weeks of drug and instructions for dosing.

6.2.6 Week 20 Telephone Visit – OLE

This visit will take place in-person 140 ± 3 days after the Week 24 Visit of the placebo-controlled portion of the trial. The procedures listed in the SoA should be performed.

6.2.7 Week 24 Telephone Visit – OLE

This visit will take place 196 ± 3 days after the Week 24 Visit of the placebo-controlled portion of the trial via telephone. The procedures listed in the SoA should be performed.

6.2.8 Week 28 Visit and Q12 Weeks – OLE

Participants should be instructed to skip the morning dose of study drug on the day of the study visit. Study drug should not be taken until after study visit procedures are complete.

This visit will take place in-person 196 ± 14 days after the Week 24 Visit of the placebo-controlled portion of the trial. The procedures listed in the SoA should be performed and participants should be provided with 8 weeks of drug and instructions for dosing. Following the Week 28 OLE Visit, visit will occur every 12 weeks ± 14 days.

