|--|----------------|----------------------|----------------------|----------------------|----------------------|--------------------------|------------------------|------------------------|--|---------------------------------------|
| Activity | Week 24 Visit | Week 2 ¹ | Week 4 ¹¹ | Week 8 ¹¹ | Week 12 | Week 16 ^{10,11} | Week 20 | Week 24 | Week 28 ^{10,11} and Q12 weeks | Follow-up Safety Call ^{3,4} |
| | Clinic | Phone | Clinic | Clinic | Phone | Clinic | Phone | Phone | Clinic | Phone |
| | Day 0 | Day 14 _{±3} | Day 28 _{±7} | Day 56 _{±7} | Day 84 _{±3} | 112 _{±7} days | 140 _{±3} days | 168 _{±3} days | Q12 weeks _{±14} days | 28 _{±7} days after last dose |
| Vital Signs ⁵ | X | | X | X | | X | | | X | |
| Slow Vital Capacity | X | | X | X | | X | | | X | |
| Home Spirometry | | | X | X | | X | | | X | |
| Muscle Strength Assessment | X | | | | | | | | | |
| ALSFRS-R | X | | X | X | X | X | X | X | X | |
| ALSAQ-40 | X | | | | | | | | X ¹⁴ | |
| CNS bulbar Function Scale | X | | | X | | X | | | X | |
| 12-Lead ECG | X | | X | | | | | | X ¹³ | |
| Clinical Safety Labs ⁶ | X | | X | X | | X | | | X | |
| Biomarker Blood Collection | X | | | | | X | | | X ¹² | |
| Verdiperstat (BHV-3241 specific PD biomarkers ⁷) | X | | | | | X | | | X ¹² | |
| PK Blood Collection ⁷ | X | | | | | X | | | X ¹² | |
| Biomarker Blood Collection | X | | | | | X | | | X ¹² | |
| Biomarker Urine Collection | X | | | | | X | | | X ¹² | |
| Concomitant Medication Review | X | X | X | X | X | X | X | X | X | |
| Adverse Event Review | X | X | X | X | X | X | X | X | X | X |
| Columbia-Suicide Severity Rating Scale | X | | X | X | | X | | | X | |
| Administer/Dispense Investigational product | X ⁸ | | X | X | | X | | | X ¹⁵ | |
| Drug Accountability/Compliance | X | X ¹⁶ | X | X | X ¹⁶ | X | X ¹⁶ | X ¹⁶ | X | |
| Dose Escalation | | X ⁹ | | | | | | | | |

HEALEY ALS Platform Trial
 Regimen-Specific Appendix B, Verdiperstat
 Version 6.0 , 02-December-2021
 CONFIDENTIAL

¹ At the end of Week 2, an assessment of compliance and tolerance to this dose titration schedule will be conducted. The assessment will be conducted by phone. If tolerability issues are experienced with 300 mg QD or 300 mg BID dosing, the titration schedule may be modified (see Section 5.3.2).

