² The last visit for the open-label extension will be at Week 52. Participants who withdraw consent or terminate early (prior to Week 52) from the study will be asked to be seen for an in-person Early Termination Visit and should have the same procedures as the Week 52 visit.

³ Participants who continue into the OLE and then early terminate will be asked to complete an Early Termination Visit and Follow-Up Safety Call as described in the body of this RSA.

⁴ Participants will have a Follow-up Safety Call approximately 28 days after the last dose of study drug. At this call, information on clinical status should be collected.

⁵ Vital signs include weight, systolic and diastolic pressure, respiratory rate, heart rate and temperature.

⁶ Clinical safety labs include hematology (CBC with differential), complete chemistry panel, liver function tests, thyroid function (TSH) and urinalysis. Serum pregnancy testing will occur in women of child-bearing potential at the Master Protocol Screening Visit and as necessary during the study. Pregnancy testing is only repeated as applicable if there is a concern for pregnancy.

⁷ Myeloperoxidase protein and activity, and plasma concentrations of verdiperstat will be measured. For each sample, the time of the last verdiperstat dose prior to sample collection, time of the last meal prior to sampling, and time of the PD/PK sample collection should be reported on the CRF.

⁸ Administer first dose of investigational product (IP) only after Week 24 procedures are completed. Participants should take the first dose of IP while in the office/clinic on the day of the Week 24 visit and stay at the clinic for approximately 30 minutes post-dose for observation.

⁹ From start to end of Week 1, participants will ingest 300 mg QD of verdiperstat QD. From start to end of Week 2, participants will ingest 300 mg BID of verdiperstat BID. Starting with Week 3 and continuing to Week 52, participants will ingest 600 mg BID of verdiperstat BID.

¹⁰ Participants should be instructed to skip the morning dose of study drug on the day of the study visit – at OLE Weeks 16, 28 and 52. Study drug should not be taken until after study visit procedures are complete.

¹¹ Visit may be conducted via phone or telemedicine with remote services instead of in-person if this is needed to protect the safety of the participant due to a pandemic.

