6.1.9 Week 24 Visit or Early Termination Visit

Participants should be instructed to skip the morning dose of study drug on the day of the study visit. Study drug should not be taken until after study visit procedures are complete.

The Week 24 Visit will take place in-person 168 ± 7 days after the Baseline Visit. The following procedures will be performed at either the Week 24 Visit or the Early Termination Visit for the regimen schedule:

- Home Spirometry
- ALSAQ-40
- CNS Bulbar Function Scale
- Collection of plasma samples for verdiperstat PD biomarkers (MPO protein and activity) and a plasma PK sample
- Voice Recording
- Uninstall Smartphone App
- Dispense IP (only if continuing in OLE)
- Remind participant to bring IP to the next visit

For participants rolling into the OLE, all participants should be instructed to follow the dose escalation scheme.

- After all Week 24 procedures are completed, administer a single 300 mg tablet of verdiperstat. Participants should stay at the clinic for approximately 30 minutes for observation.
- Dispense study drug to last for the next 4 weeks.
- Participants should be instructed:
 - To ingest 300 mg QD of BHV-3241 for the rest of Week 1.
 - To ingest 300 mg BID of BHV-3241 starting at the beginning of Week 2. Participants should take the study drug twice a day; dosing in the morning and evening approximately 12 hours apart.
 - If tolerability issues are experienced with 300 mg QD or 300 mg BID dosing, the titration schedule may be modified (see Section 5.3.2).
 - To ingest 600 mg BID of BHV-3241 starting at the beginning of Week 3 and through the remainder of the 52-week OLE. Participants should take the study drug twice a day; dosing in the morning and evening approximately 12 hours apart.

For participants NOT rolling into the OLE:

A Follow-up Safety Call should be scheduled approximately 28 days after last dose of study drug to collect clinical status information.

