8 BIOFLUID COLLECTION

8.2 Pharmacokinetic Assessments

Blood samples for PK analysis should be collected at Baseline and Weeks 4, 8, 16, and 24 in the Treatment Phase, and at Weeks 16, 28, and 52 for participants who are in the OLE. Participants who discontinue early from study medication are not required to have PK samples collected at the early discontinuation visit.

A PK sample should be collected pre-dose at the Baseline visit.

At Weeks 4, 8, 16, and 24 in the Treatment Phase, and at Weeks 4, 16, 28, 40, and 52 in the OLE, the morning dose of study drug should be held and administered in the clinic/office during the study visit, so that one pre-dose (trough) PK sample can be collected. For each sample, the time of the last dose of study drug prior to sample collection, time of the last meal, and time of collection of the PK samples should be reported on the CRF.

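### Protocol Section 6.2.8 gives 8 weeks of drug at OLE Week 28, but the next dispensing visit is 12 weeks later: a nominal 28-day shortfall against continuous 600 mg BID dosing

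*Protocol*

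**What the plan says.** Section 6.2.8 of the Protocol (Regimen-Specific Appendix B) covers the OLE Week 28 visit and the 12-weekly visits after it. Participants at Week 28 are to be "provided with 8 weeks of drug and instructions for dosing. Following the Week 28 OLE Visit, visit will occur every 12 weeks", with a window of ±14 days.

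Section 6.2 confirms which clinic visit follows Week 28. It lists "Designated visits in the Schedule of Activities for the OLE (i.e. Week 4, Week 8, Week 16, Week 28, and Week 40" as the visits that may be held remotely.

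In the OLE Schedule of Activities, the row "Administer/Dispense Investigational product" is marked at the Week 24 Visit (OLE Day 0), at OLE Weeks 4, 8 and 16, and in the column for Week 28 and every 12 weeks. No phone visit is marked for dispensing. Footnote 15 makes one exception, the participant's final in-clinic visit.

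Footnote 9 to the same schedule sets the dose: "Starting with Week 3 and continuing to Week 52, participants will ingest 600 mg BID of verdiperstat BID".

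Quantities are also given for the earlier OLE visits:

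- Section 6.1.9, OLE Day 0: "Dispense study drug to last for the next 4 weeks".
- Section 6.2.2, OLE Week 4: "participants should be provided with 4 weeks of drug and instructions for dosing".
- Section 6.2.3, OLE Week 8: "participants should be provided with 8 weeks of drug and instructions for dosing".
- Section 6.2.5, OLE Week 16: a 12-week supply.

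**The concern.** The quantity and the visit interval stand in adjacent sentences of Section 6.2.8 and do not match. A participant who takes 600 mg BID as instructed uses up an 8-week supply four weeks before the next scheduled dispensing. The schedule lists no phone visit after OLE Week 24, so no scheduled contact would pick up the run-out before Week 40.

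What is at stake is an unplanned interruption of treatment for people with ALS. Under Section 5.4, anyone off drug for more than 14 consecutive days should re-escalate using the Section 5.3.1 titration. That adds one week at 300 mg QD and one at 300 mg BID before full dose resumes. Safety labs are scheduled in the 12-weekly column, so the Week 40 sample could be taken after some weeks without drug.

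**Working it through.** **Inputs.** Dispensing visits come from the OLE Schedule of Activities. Quantities come from Sections 6.1.9, 6.2.2, 6.2.3, 6.2.5 and 6.2.8. The Week 40 visit comes from Sections 6.2 and 6.2.8. Tablet strength is 300 mg (Section 5), so 600 mg BID is 2 × 2 = 4 tablets per day.

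**Step 1: find the rule the plan follows.** Shortfall = weeks to the next dispensing visit − weeks supplied.

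| OLE dispensing visit | Next dispensing visit | Interval (weeks) | Supply (weeks) | Shortfall (weeks) |
|---|---|---|---|---|
| Day 0 | Week 4 | 4 | 4 | 0 |
| Week 4 | Week 8 | 4 | 4 | 0 |
| Week 8 | Week 16 | 8 | 8 | 0 |
| Week 16 | Week 28 | 12 | 12 | 0 |
| Week 28 | Week 40 | 12 | 8 | 4 |

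Setting supply equal to the nominal interval reproduces the first four quantities exactly. At Week 28 the same rule gives 12, not the stated 8. The Week 16 row shows that the plan already dispenses 12 weeks of drug at once when the interval is 12 weeks.

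**Step 2: size of the gap at nominal visit days.**

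- Days needed: 12 × 7 = 84. Days supplied: 8 × 7 = 56. Shortfall: 84 − 56 = 28 days.
- On the calendar: Week 28 is Day 196, and the supply ends at 196 + 56 = Day 252 (Week 36). Week 40 is Day 280, and 280 − 252 = 28 days.
- Tablets at 600 mg BID: 84 × 4 = 336 needed, 56 × 4 = 224 supplied, 336 − 224 = 112 short.

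**Step 3: compare with Section 5.4.** The nominal gap of 28 days is longer than the 14 consecutive days after which re-escalation applies.

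**Step 4: effect of the correction.** With 12 weeks supplied, 84 − 84 = 0 days short at the nominal interval. If the next visit falls 14 days late, the interval is 84 + 14 = 98 days (14 weeks), which needs 98 × 4 = 392 tablets.

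**The case against.** The strongest reply is that this is a one-word slip in an optional, uncontrolled extension. SAP Section 1 confines that plan to the placebo-controlled period, so none of its analyses depends on OLE Week 40. Section 6.2.8 also sets no ceiling on supply and does not forbid an interim resupply. The Manual of Procedures governs drug accountability (Section 5.2.3) and dispensing at remote visits (Section 6), and it is not among the documents. Sites may have dispensed enough drug. All of this stands as a limit on the consequences. It does not repair the Protocol text, which states a quantity that does not cover its own interval and mentions no resupply.

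A reader might infer more than the documents support in five ways:

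- **That safety signals would be missed at Week 40.** Section 5.9.1.1 says thyroid changes moved back toward baseline after stopping, but gives no time course. The recovery within weeks in Section 5.9.1.4 concerns four participants in a study that was still blinded. Neither shows that a 28-day gap would hide an abnormality.
- **That Section 8.2 proves drug must be in hand at Week 40.** It says that "at Weeks 4, 16, 28, 40, and 52 in the OLE, the morning dose of study drug should be held". Footnote 10 to the OLE schedule limits the hold to Weeks 16, 28 and 52, so the two conflict and the point should not rest on Section 8.2.
- **That visit windows give a range for the Week 28 gap.** Windows can stretch earlier intervals too. Week 16 (Day 112 ± 7) to Week 28 (Day 196 ± 14) can reach 210 − 105 = 105 days against 84 supplied. Windows are therefore not specific to this error, and only the nominal 28 days measures it.
- **That Week 40 is the only check that could be reached without drug.** The same 105-day example shows that this cannot be claimed.
- **That the gap recurs at every later visit.** The section heading covers the 12-weekly visits, but no separate quantity is given for them. The text firmly supports one gap, from Week 28 to Week 40.

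**Conclusion.** The quantity in Section 6.2.8 is wrong as written. It conflicts with the 12-week interval in the next sentence, with continuous 600 mg BID dosing, and with the rule followed at all four earlier OLE dispensing visits. The natural reading is that 8 should be 12. Followed literally, it leaves a nominal 28 days without drug (112 tablets), twice the 14-day limit in Section 5.4, and re-escalation would follow.

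This rests on visits at their nominal days, full adherence at 600 mg BID, no tablets left over from earlier dispensing, and no resupply between visits. Leftover tablets from missed or reduced doses would shorten the gap for some participants, but they are not a planned supply. That Week 40 labs might be drawn off drug is a possibility, not a demonstrated loss of safety information. The 24-week placebo-controlled efficacy and safety analyses are not touched. The documents do not show whether any participant actually went without drug.

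**What to change.** In Section 6.2.8, change the Week 28 supply from 8 weeks to 12 weeks (336 tablets at 600 mg BID). Add that the same quantity is dispensed at each later 12-weekly visit except the participant's final in-clinic visit, consistent with footnote 15. This closes the nominal gap. If the sponsor also wants to cover a visit 14 days late, the quantity is 14 weeks (392 tablets).

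The cost is one line in the Protocol, any matching line in the Manual of Procedures or Pharmacy Manual, and 112 more tablets per participant at Week 28 than the text now provides (168 more, 392 − 224, for the 14-week option). No analysis changes.

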7 OUTCOME MEASURES AND ASSESSMENTS

For all assessments listed below, please refer to the Manual of Procedures for detailed instructions.

7.1 Voice Analysis

Voice samples will be collected twice per week, using an app installed on either an android or iOS based smartphone. The app characterizes ambient noise, then asks participants to perform a set of speaking tasks: reading sentences -- 5 fixed and 5 chosen at random from a large sentence bank-- repeating a consonant-vowel sequence, producing a sustained phonation, and counting on a single breath. Voice signals are uploaded to a HIPAA-compliant web server, where an AI-based analysis identifies relevant vocal attributes. Quality control (QC) of individual samples will occur by evaluation of voice records by trained personnel.

The voice analysis app is only available in English, therefore participants who do not speak English should not complete the voice recording. Caregivers cannot provide language assistance when the participant is completing the voice recording.

7.2 ALSAQ-40

The Amyotrophic Lateral Sclerosis Assessment Questionnaire-40 (ALSAQ-40) is a patient self-report health status patient-reported outcome. The ALSAQ-40 consists of forty questions that are specifically used to measure the subjective well-being of patients with ALS and motor neuron disease.

Participants will be handed the questionnaire and asked to write their answers themselves. Caregivers can also help, if needed.

7.3 Center for Neurologic Study Bulbar Function Scale

The Center for Neurologic Study Bulbar Function Scale (CNS-BFS) is a patient self-report scale that has been developed for use as an endpoint in clinical trials and as a clinical measure for evaluating and following ALS patients. The CNS-BFS consists of three domains (swallowing, speech, and salivation), which are assessed with a 21-question, self-report questionnaire.

Participants will be handed the questionnaire and asked to write their answers themselves. Caregivers can also help, if needed.

Instructions on administering the questionnaire during a phone or telemedicine visit will be included in the MOP.

7.4 Home Spirometry

Remote/home-based forced vital capacity will be measured with the MIR Spirobank Smart spirometer. Instructions for use will be provided to the participant. The participant will perform the vital capacity maneuver at home with real time video coaching (or phone coaching, if video is not available) by the evaluator. Three to five vital capacity maneuvers will be performed, consistent with the manner vital capacity is obtained in clinic.

8 BIOFLUID COLLECTION

8.2 Pharmacokinetic Assessments

Blood samples for PK analysis should be collected at Baseline and Weeks 4, 8, 16, and 24 in the Treatment Phase, and at Weeks 16, 28, and 52 for participants who are in the OLE. Participants who discontinue early from study medication are not required to have PK samples collected at the early discontinuation visit.

A PK sample should be collected pre-dose at the Baseline visit.

At Weeks 4, 8, 16, and 24 in the Treatment Phase, and at Weeks 4, 16, 28, 40, and 52 in the OLE, the morning dose of study drug should be held and administered in the clinic/office during the study visit, so that one pre-dose (trough) PK sample can be collected. For each sample, the time of the last dose of study drug prior to sample collection, time of the last meal, and time of collection of the PK samples should be reported on the CRF.

